**Table 5.3.2 Definition of notable ranges for vital signs and weight**

|                          |   |
|--------------------------|---|
| Systolic blood pressure  | ≥180 mmHg / ≤90 mmHg with increase / decrease from baseline of ≥20 mmHg |
| Diastolic blood pressure | ≥105 mmHg / ≤50 mmHg with increase / decrease from baseline of ≥15 mmHg |
| Pulse rate               | ≥120 bpm / ≤50 bpm with increase / decrease from baseline of ≥15 bpm    |
| Weight                   | ≥7% increase or decrease from baseline weight                           |

## 5.4 Statistical models

### 5.4.1 Primary analysis

#### SAS code for Mc Nemar's test

```
proc freq data=;
    table p12*p21;
    exact mcnem;
    weight patients;
run;
```

p12 and p21 respectively denote the proportion of patients with preference of FCT over DT and vice versa.

## 5.4.2 Secondary analysis

### SAS code for Homogeneity test:

```
proc freq data=;  
tables Drug_A Drug_B Drug_C / nocum;  
tables Drug_A*Drug_B*Drug_C / agree noprint;  
format Drug_A Drug_B Drug_C $ResponseFmt. ;  
weight Count;  
title 'xxxxxxx';  
run; Drug_A=FCT, Drug_B= DT and Drug_C= iron chelation
```

### SAS code for ANCOVA

```
proc glm data = ;  
class treatmentgroups;  
model compliance = treatmentgroups agegroup thalassemiatransdep;  
run;  
quit;
```

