10.5.2 Other secondary efficacy objectives

The following secondary analyses will be performed:

Patient preference of FCT, DT, and iron chelation at Week 28

Proportion and percentage, % (and 95% CI) of patients with preference and non-preference of FCT over DT, FCT over iron chelation, and DT over iron chelation will be summarized separately at Week 28.

Homogeneity test (Cochran's Q test) may be performed to check the homogeneity of the three preferences. Exact and asymptotic p-values of Mc Nemar's test will also be presented as analogous to primary analysis, for each pair of treatment comparison. For comparison of FCT

and DT with iron-chelation, only patients who are pre-treated with iron chelation will be selected.

Patient preference of DT and iron chelation at Week 4 and Week 24

Proportion and percentage, % (and 95% CI) of patients with preference and non-preference of DT over iron chelation will be summarized at Week 4 and Week 24. Exact and asymptotic p-values of Mc Nemar's test will also be presented as analogous to primary analysis. Only patients who are pre-treated with iron-chelation will be considered.

Reasons of patient preference

The reasons or factors influencing behind patient preference of FCT over DT will be summarized at Week 28 and 48. Proportions of patients for selecting each reason will be presented for each study treatment. Further summary of reasons behind non-preference of each study treatment will also be presented.

Compliance using pill count

Compliance is measured by pill /tablet count based on amount of medication dispensed, returned and reported as lost/wasted by the patient or caregiver. Compliance will be calculated for each treatment (FCT: Week 25- Week 48, DT: Baseline day 1 – Week 24) as the ratio of total count consumed to total count prescribed, where

total count consumed is derived from cumulative dispensed, returned and lost/wasted counts;

- total count prescribed is cumulative prescribed count

Analysis of covariance (ANCOVA) will be performed for comparison between both treatment groups (FCT and DT). The ANCOVA model for compliance endpoint will include treatment group and age group ((2 to <6 years, 6 to <10 years, 10 to <18 years, and ≥ 18 years) and thalassemia transfusion dependence (transfusion and non-transfusion dependent) as factors. Least squares estimates, 95% CI and p-value will be presented for each treatment and difference between treatments.

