### **2.7.2 Statistical hypothesis, model, and method of analysis**

No formal hypothesis testing will be conducted for secondary endpoints.

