**Compliance using pill count**

Compliance is measured by pill/tablet count based on amount of medication dispensed, returned and reported as lost/wasted by the patient or caregiver. Compliance will be calculated for each treatment (FCT: Week 25- Week 48, DT: Baseline day 1 – Week 24) as the ratio of total count consumed to total count prescribed, where total count consumed is derived from cumulative dispensed, returned and lost/wasted counts and total count prescribed is the cumulative prescribed count.

The prescribed count corresponds to the count prescribed by the investigator for a period that the patient should have taken during this period. For each strength (125 mg, 250 mg and 500 mg tablets for Deferasirox DT; 90 mg, 180 mg and 360 mg tablets for Deferasirox FCT), the prescribed count for a period is calculated from the daily prescribed count at the beginning of this period multiplied by the duration (days) of this period. The daily prescribed count is the sum of counts prescribed per strength. The duration of a period will be calculated as (end date of the period) – (start date of the period) + 1. The following period duration calculation will exclude the start day. The total count prescribed is the sum of counts prescribed over all periods.

If a patient does not return the study drug, the compliance will not be calculated.

Analysis of covariance (ANCOVA) will be performed for comparison between both treatment groups (FCT and DT). The ANCOVA model for compliance endpoint will include treatment group and age group (2 to < 6 years, 6 to < 10 years, 10 to < 18 years, and  $\geq$  18 years) and thalassemia transfusion dependence (TDT and NTDT) as factors. Least squares estimates, 95% CI and p-value will be presented for each treatment and difference between treatments.

Summary statistics of number of pills (and percentages) will also be presented overall and by treatment and subgroups.

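### The printed compliance ANCOVA code does not fit the model in the SAP and protocol text: age group is outside CLASS and no least-squares means are requested

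*SAP*

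**What the plan says.** SAP 2.7.2, under Compliance using pill count, sets out the model: "The ANCOVA model for compliance endpoint will include treatment group and age group", with four age bands (2 to under 6, 6 to under 10, 10 to under 18, and 18 years or older), "and thalassemia transfusion dependence (TDT and NTDT) as factors". Protocol 10.5.2 gives the same model and the same role for the terms: "and thalassemia transfusion dependence (transfusion and non-transfusion dependent) as factors". Both documents ask for the same output, which the SAP words as "Least squares estimates, 95% CI and p-value will be presented for each treatment and difference between treatments".

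SAP 5.4.2, under SAS code for ANCOVA, prints a PROC GLM block. Its CLASS statement is "class treatmentgroups" and its MODEL statement is "model compliance = treatmentgroups agegroup thalassemiatransdep". Nothing else in the block requests estimates: there is no LSMEANS, ESTIMATE, SOLUTION or CLPARM.

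Two points of context. SAP 2.7.2 opens with "No formal hypothesis testing will be conducted for secondary endpoints", so the compliance p-value is descriptive. SAP section 4 declares no change to the protocol's analyses, so the code is not presented as a deliberate departure.

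**The concern.** In PROC GLM, a MODEL variable that is not named in CLASS is treated as a numeric regressor. The block therefore does not fit the factor model described in the text. With numeric codes, four age bands are forced onto a straight line in the code value. With text values, the procedure stops. Even when it runs, it gives F tests but no adjusted mean per treatment, no interval for either treatment and no interval for the difference.

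The promised compliance table is at stake. A programmer who follows the appendix literally would fit a different model from the one in the protocol and would have to improvise the estimates. If age matters for compliance in a non-linear way, for example with a dip in adolescence, the misfit goes into the residual variance.

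**Working it through.** The plan gives no sample size, power or variance for this analysis, so there is no figure to reproduce. The check has three parts.

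**1. Text against code**

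| Item | SAP 2.7.2 and protocol 10.5.2 | SAP 5.4.2 code |
|---|---|---|
| Treatment | factor, 1 df | CLASS, 1 df |
| Age group | factor, 4 levels, 3 df | not in CLASS, 1 df if numeric |
| Transfusion status | factor, 2 levels, 1 df | not in CLASS, 1 df if numeric |
| Model df | 1 + 3 + 1 = 5 | 1 + 1 + 1 = 3 |
| Estimate, CI and p-value per treatment | required | not requested |
| Estimate and CI for the difference | required | not requested |

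The behaviour of PROC GLM is stated from how the procedure works; SAS was not run.

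**2. Size, by illustration**

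The protocol's planned 145 patients are used. All other inputs are assumptions: age-band probabilities 0.2, 0.2, 0.3 and 0.3; mean compliance by band 0.95, 0.97, 0.80 and 0.92 (non-linear); 20% and 80% in the two transfusion groups; FCT effect 0.03; patient SD 0.05 and residual SD 0.05. One simulated data set was fitted by least squares without a patient term, as the plan has it, and again with a random patient term.

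| Complete pairs (290 records) | FCT-DT | SE, no patient term | SE, patient term |
|---|---|---|---|
| Age and transfusion status numeric (as coded) | 0.0360 | 0.0107 | 0.0061 |
| All terms as factors (as in the text) | 0.0360 | 0.0081 | 0.0061 |
| Age numeric, transfusion status as factor | 0.0360 | 0.0107 | 0.0061 |

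- Without a patient term the SE ratio is 0.0107 / 0.0081 = 1.32.
- A second set of assumed inputs (137 patients; age bands of 12, 20, 35 and 70; age effects of up to 12 percentage points) gave SEs for factor against linear age of 0.60 v 0.79, 0.96 v 1.09 and 1.20 v 1.31 at residual SDs of 5, 8 and 10. The ratios are 1.32, 1.14 and 1.09.
- With an exactly linear age effect (band means 0.98, 0.94, 0.90 and 0.86), the SE was 0.0085 under both codings.
- With a patient term and complete pairs the coding makes no difference, because age group is constant within a patient and cancels from the FCT minus DT contrast. The SE of the simple paired difference is also 0.0061.
- Changing only transfusion status from numeric to factor left the difference and its SE unchanged.

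**Incomplete pairs.** SAP 2.7.2 does not calculate compliance when drug is not returned, so some patients may contribute one period only. Assuming FCT records are lost in 35% of the third age band and 5% of the others, the unpaired difference was 0.0383 as coded and 0.0315 with factors. With a patient term it was 0.0345 and 0.0314.

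**3. Adjusted means (complete pairs, non-linear case)**

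| Fit and weighting | DT | FCT |
|---|---|---|
| Numeric covariates held at their means | 0.8877 | 0.9237 |
| Factors, weighted by the enrolled mix | 0.8877 | 0.9237 |
| Factors, equal weight per level | 0.8951 | 0.9311 |

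The gap between the first and last rows comes from the weighting: factor coding with the enrolled mix reproduces the numeric-covariate means.

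**The case against.** The strongest reply is that the practical risk is low. The text states the intended model twice and without ambiguity. The code is a skeleton with a blank data set name. Text-coded variables would produce an error that someone would notice. Compliance is secondary and not formally tested. All of this stands, and it keeps the point minor. It does not remove the mismatch: the forest-plot and Kaplan-Meier blocks are labelled as examples, this one is not, and its CLASS and MODEL statements are complete enough to copy.

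The reply is also right that several stronger readings do not hold:

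- A reader might infer that the trial's interval for FCT-DT will be 9% to 32% too wide. Those figures rest on assumed age effects and variances that the documents do not give, and on the unpaired fit. They fall to zero if the age effect is linear, or with a patient term and complete pairs.
- A reader might infer that the code reports wrong treatment means. It reports none, and the shift in means reflects equal against observed weighting, which neither document specifies.
- A reader might infer that transfusion status is misfitted in the same way. With two levels it uses 1 df under either coding.
- A reader might infer bias in the treatment difference. With complete pairs there is none. It moved only under an assumed age-dependent loss of FCT records, and the full analysis set already requires a dose of each formulation.

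**Conclusion.** The point holds as a specification error in the code. SAP 5.4.2 does not implement the compliance model in SAP 2.7.2 and protocol 10.5.2. A numeric age group would get 1 df instead of 3, text-coded variables would stop the run, and the required per-treatment estimates, intervals and p-values and the interval for the difference would not be produced. This conclusion needs no assumption beyond how PROC GLM treats variables outside CLASS.

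The numerical effect is conditional. Under the unpaired model as printed, a non-linear age effect would enter the error term and could widen the interval for the difference, by an amount that the documents do not allow anyone to fix. Severity is minor: a correction worth making before programming, with no bearing on the primary analysis.

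**What to change.** Replace the CLASS statement with `class treatmentgroups agegroup thalassemiatransdep;` and add `lsmeans treatmentgroups / stderr pdiff cl;`. STDERR supplies the per-treatment p-values that the text asks for; PDIFF and CL supply the p-value and interval for the difference and the intervals for the means.

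Add one sentence to SAP 2.7.2 stating whether the means weight the levels equally (the default) or by observed margins (the OM option). The default has a small downside: each age band gets a quarter of the weight however few patients it holds.

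The cost is two lines of code and one sentence, with no change to the stated method. This does not deal with the pairing of each patient's DT and FCT values. Neither the text nor the code has a patient term, and that needs its own decision.

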### Example SAS Code for Forest plot

```
%let gpath='C:\';  
%let dpi=200;  
  
data ae;  
input Pref $1-30 NA NB SNA SNB;  
datalines;  
ABDOMINAL PAIN 20 61 216 431  
ANOREXIA 2 15 216 431  
ARTHRALGIA 1 15 216 431  
BACK PAIN 10 23 216 431  
BRONCHITIS 8 11 216 431  
CHEST PAIN 9 12 216 431  
CHRONIC OBSTRUCTIVE AIRWAY 76 95 216 431  
COUGHING 13 26 216 431  
DIARRHEA 23 90 216 431  
DIZZINESS 9 29 216 431  
DYSPEPSIA 8 42 216 431  
DYSPNEA 15 9 216 431  
FATIGUE 4 16 216 431  
FLATULENCE 6 20 216 431  
GASTROESOPHAGEAL REFLUX 5 12 216 431  
HEADACHE 14 36 216 431  
HEMATURIA 2 14 216 431  
HYPERKALEMIA 4 9 216 431  
INFECTION VIRAL 12 26 216 431  
INJURY 12 30 216 431
```

|                            |    |    |     |     |
|----------------------------|----|----|-----|-----|
| INSOMNIA                   | 4  | 26 | 216 | 431 |
| MELENA                     | 7  | 12 | 216 | 431 |
| MYALGIA                    | 6  | 12 | 216 | 431 |
| NAUSEA                     | 10 | 82 | 216 | 431 |
| PAIN                       | 4  | 17 | 216 | 431 |
| RASH                       | 4  | 9  | 216 | 431 |
| RESPIRATORY DISORDER       | 4  | 11 | 216 | 431 |
| RHINITIS                   | 11 | 17 | 216 | 431 |
| SINUSITIS                  | 13 | 28 | 216 | 431 |
| UPPER RESP TRACT INFECTION | 33 | 68 | 216 | 431 |
| URINARY TRACT INFECTION    | 6  | 12 | 216 | 431 |
| VOMITING                   | 6  | 37 | 216 | 431 |
| WEIGHT DECREASE            | 2  | 9  | 216 |     |

run;

```
/*--Compute Proportions for treatment A & B, Mean and Risk--*/
```

```
data ae_risk;
```

```
  set ae;
```

```
  keep pref a b mean lcl ucl;
```

```
  a=na/sna;
```

```
  b=nb/snb;
```

```
  factor=1.96*sqrt(a*(1-a)/sna + b*(1-b)/snb);
```

```
  lcl=a-b+factor;
```

```
  ucl=a-b-factor;
```

```
  mean=0.5*(lcl+ucl);
```

run;

```
/*--Sort by mean value--*/
```

```
proc sort data=ae_risk out=ae_sort;
```

```
  by mean;
```

run;

```
/*--Add alternate reference lines--*/
```

```
data ae_ref;
```

```
  set ae_sort;
```

```
  if mod(_n_, 2) eq 0 then ref=pref;
```

run;

```
proc print;run;
```

```
/*--Create template for AE graph--*/
```

```
proc template;
```

```
  define statgraph AEbyRelativeRisk;
```

```
    dynamic _thk _grid;
```

```
    begingraph;
```

```
      entrytitle 'Most Frequent On-Therapy Adverse Events Sorted by Risk Difference';
```

```
      layout lattice / columns=2 rowdatarange=union columngutter=5;
```

```
        /*--Row block to get common external row axes--*/
```

```
        rowaxes;
```

```
          rowaxis / griddisplay=_grid display=(tickvalues)
```

```
tickvalueattrs=(size=5);
```

```
        endrowaxes;
```

```
        /*--Column headers with filled background--*/
```

```
        column2headers;
```

```
        layout overlay / border=true backgroundcolor=cxdfdfdf opaque=true;
            entry "Proportion";
        endlayout;
        layout overlay / border=true backgroundcolor=cxdfdfdf opaque=true;
            entry "Risk Difference with 0.95 CI";
        endlayout;
    endcolumn2headers;

    /*--Left side cell with proportional values--*/
    layout overlay / xaxisopts=(display=(ticks tickvalues)
    tickvalueattrs=(size=7));
        referenceline y=ref / lineattrs=(thickness=_thk)
    datatransparency=0.9;
        scatterplot y=pref x=a /
    markerattrs=graphdata2(symbol=circlefilled)
            name='a' legendlabel="Treatment (N=&NA)";
        scatterplot y=pref x=b /
    markerattrs=graphdata1(symbol=trianglefilled)
            name='b' legendlabel="Control (N=&NB)";
    endlayout;

    /*--Right side cell with Relative Risk values--*/
    layout overlay / xaxisopts=(label='Less Risk'                                More
    Risk'
            labelattrs=(size=8) tickvalueattrs=(size=7));
        referenceline y=ref / lineattrs=(thickness=_thk)
    datatransparency=0.9;
        scatterplot y=pref x=mean / xerrorlower=lcl xerrorupper=ucl
            markerattrs=(symbol=circlefilled size=5);
        referenceline x=0 / lineattrs=graphdatadefault(pattern=shortdash);
    endlayout;

    /*--Centered side bar for legend--*/
    sidebar / spacefill=false;
        discretelegend 'a' 'b' / border=false;
    endsidebar;
    endlayout;
endgraph;
end;
run;

ods html close;
ods listing gpath=&gpath image_dpi=&dpi style=listing;

/*--Render the graph with grid lines without horizontal bands--*/
ods graphics / reset width=6in height=4in imagename='AEbyRelativeRisk';
proc sgrender data=ae_ref template=AEbyRelativeRisk;
    dynamic _thk='0' _grid='on';
run;

/*--Render the graph without grid lines and with horizontal bands--*/
ods graphics / reset width=6in height=4in imagename='AEbyRelativeRiskRef';
proc sgrender data=ae_ref template=AEbyRelativeRisk;
    dynamic _thk='9' _grid='off';
run;
```

# Here you have to creat a dataset for SOC with counts for DT and FCT and then proceed.

### Example code for Kaplan-Meier and Logrank test

```
proc lifetest data=BMT
plots=survival(atrisk(outside(0.15)));
time T * Status(0);
strata Group / order=internal;
format group bmtfmt.;
run;

ods graphics on;

proc lifetest data=Exposed plots=(survival(atrisk) logsurv);
time Days*Status(0);
strata Treatment;
run;

ods graphics off;
```

## 5.5 Rule of exclusion criteria of analysis sets

**Table 1 Protocol deviations that cause subjects to be excluded**

| Deviation ID | Description of Deviation  | Exclusion in Analyses    | Severity code |
|--------------|---|--------------------------|---------------|
| D02          | Patient enrolled correctly but did not receive any study treatment and not withdrawn.   | EXCLUDE FROM FAS AND SAF | 3             |
| D03          | Pregnancy occurred while pt actively participating in study. Study drug was administered after notice of pregnancy and the pt was NOT discontinued from the study.                      | EXCLUDE FROM PPS         | 4             |
| D04          | Patients not discontinued from study despite is fulfilling the discontinuation criteria as per protocol section 7.1.3.1 and 7.1.3.2.  | EXCLUDE FROM PPS         | 4             |
| E01          | Creatinine clearance below the contraindication limit in the locally approved prescribing information. Creatinine clearance will be estimated from serum creatinine at screening visit. | EXCLUDED FROM PPS        | 4             |
| E02          | Serum creatinine > 1.5 x ULN at screening measured at screening visit.  | EXCLUDED FROM PPS        | 4             |
| E03a         | ALT (SGPT) > 5 x ULN unless LIC >10mg Fe/dw within 6 months prior to screening visit  | EXCLUDED FROM PPS        | 4             |

| Deviation ID | Description of Deviation  | Exclusion in Analyses | Severity code |
|---------------------|--|------------------------------|----------------------|
| E03b                | AST (SGOT) > 5 x ULN unless LIC >10mg Fe/dw within 6 months prior to screening visit   | EXCLUDED FROM PPS            | 4                    |
| E04                 | Urinary protein / creatinine ratio >0.5 mg/mg in a non-first void urine sample at screening visit.   | EXCLUDED FROM PPS            | 4                    |
| E05                 | Patients with significant impaired gastrointestinal function that may significantly alter the absorption of oral deferasirox at screening visit.                                       | EXCLUDE FROM PPS             | 4                    |
| E06                 | Serum pregnancy test not done at visit 1 in females of child bearing potential.  | INCLUDE IN EVERYTHING        | 0                    |
| E06a                | Hepatitis B or Hepatitis C tests were not performed at visit 1.  | INCLUDE IN EVERYTHING        | 0                    |
| E07                 | Clinical or laboratory evidence of active Hepatitis B or C at visit 1.   | EXCLUDED FROM PPS            | 4                    |
| E08                 | Known history of HIV seropositivity (Elisa or Western blot).   | EXCLUDED FROM PPS            | 4                    |
| E9                  | History of malignancy of any organ system, treated or untreated, within the past 5 years (protocol section 5.3)  | EXCLUDED FROM PPS            | 4                    |
| E10                 | Patients participating in another clinical trial or receiving an investigational drug.   | EXCLUDE FROM FAS             | 1                    |
| E11                 | History of hypersensitivity to any of the study drugs or their excipients  | EXCLUDED FROM PPS            | 4                    |
| E12                 | Significant medical condition interfering with the ability to take part in this study  | EXCLUDE FROM PPS             | 4                    |
| E13                 | Female of child bearing potential unwilling to use contraception as requested by the protocol  | INCLUDE IN EVERYTHING        | 0                    |
| E14                 | Female not meeting post-menopausal criteria stated in the protocol and not using the contraception methods requested in the protocol   | INCLUDE IN EVERYTHING        | 0                    |
| E15                 | Female of child bearing potential with a positive serum pregnancy in the screening visit however subject is enrolled into the study  | EXCLUDE FROM PPS             | 4                    |
| E16                 | Sexually active males not using condom during intercourse while taking drug and for 28 days after stopping study medication  | INCLUDE IN EVERYTHING        | 0                    |
| E17                 | Patients with psychiatric or addictive disorders preventing from giving informed consent or undergoing any of the treatment options or unable or unwilling to comply with the protocol | EXCLUDE FROM FAS AND SAF     | 3                    |

| Deviation ID | Description of Deviation   | Exclusion in Analyses | Severity code |
|---------------------|---|------------------------------|----------------------|
| G01                 | Patients not completed the safety follow up evaluation  | INCLUDE IN EVERYTHING        | 0                    |
| G02a                | Patient did not complete the preference questionnaire in each period (W28 and W48)  | INCLUDE IN EVERYTHING        | 0                    |
| G02b                | Patient did not complete/partially complete the preference questionnaire at the required visits as per protocol (for W4, W24, W28 and W48)  | INCLUDE IN EVERYTHING        | 0                    |
| G02c                | Patient did not complete/partially complete the preference questionnaire at immediate next visit after unplanned treatment switch protocol. | INCLUDE IN EVERYTHING        | 0                    |
| G03                 | Do not have the pill counting information for deferasirox FCT   | INCLUDE IN EVERYTHING        | 0                    |
| G04                 | Do not have the pill counting information for deferasirox DT  | INCLUDE IN EVERYTHING        | 0                    |
| G05                 | Non-Compliance with safety/serious adverse event (SAE) reporting as per protocol.   | INCLUDE IN EVERYTHING        | 0                    |
| G06                 | Patient did not completed/partially completed the SICT, Palatability, GI symptoms questionnaire (for W1, W4, W24, W28 and W48)              | INCLUDE IN EVERYTHING        | 0                    |
| G07                 | Any protocol deviation identified non GCP compliant as per protocol.  | INCLUDE IN EVERYTHING        | 0                    |
| G08                 | Missing Lab Parameters for Lab Biochemistry at 2 consecutive Visits   | INCLUDE IN EVERYTHING        | 0                    |
| G09                 | Missing Lab Parameters for Lab Biochemistry at Visit 9 or Visit 15  | INCLUDE IN EVERYTHING        | 0                    |
| G10                 | Missing Lab Parameters for Lab Hematology at 2 consecutive Visits   | INCLUDE IN EVERYTHING        | 0                    |
| G11                 | Missing Lab Parameters for Lab Hematology at Visit 9 or Visit 15  | INCLUDE IN EVERYTHING        | 0                    |
| G12                 | Missing Lab Parameters for Lab Urinalysis at 2 consecutive Visits.  | INCLUDE IN EVERYTHING        | 0                    |
| G13                 | Missing Lab Parameters for Lab urinalysis at Visit 9 or Visit 15  | INCLUDE IN EVERYTHING        | 0                    |
| G14                 | Serum pregnancy test not done at Visit 15 in females of child bearing potential   | INCLUDE IN EVERYTHING        | 0                    |
| G15                 | Urine pregnancy test not done at Visit 2 in females of child bearing potential  | INCLUDE IN EVERYTHING        | 0                    |
| G16                 | Full visit is missing.  | EXCLUDE FROM PPS             | 4                    |
| G17                 | The visit has been performed out of protocol window.  | INCLUDE IN EVERYTHING        | 0                    |

| Deviation ID | Description of Deviation   | Exclusion in Analyses | Severity code |
|---------------------|---|------------------------------|----------------------|
| G18                 | Patient did not complete/partially complete the preference questionnaire at the immediate next visit after treatment switch.  | INCLUDE IN EVERYTHING        | 0                    |
| G19                 | Hepatitis B or Hepatitis C tests were not performed at visit 15   | INCLUDE IN EVERYTHING        | 0                    |
| G20                 | Treatment start date is outside the window period without an official medical interruption.   | EXCLUDE FROM PPS             | 4                    |
| G21                 | Ocular Examination was not performed  | INCLUDE IN EVERYTHING        | 0                    |
| G22                 | Audiometric Examination was not performed   | INCLUDE IN EVERYTHING        | 0                    |
| I01a                | ICF is not obtained from Subject.   | EXCLUDE FROM FAS AND SAF     | 3                    |
| I01b                | ICF is not obtained from Parent(s) or Legal patient(s) representative.  | EXCLUDE FROM FAS AND SAF     | 3                    |
| I01c                | Missing informed consent date for Subject.  | INCLUDE IN EVERYTHING        | 0                    |
| I01d                | Missing informed consent date from parent(s) or legal patient's representative.   | INCLUDE IN EVERYTHING        | 0                    |
| I02                 | Subject is < 2 years or age missing   | EXCLUDE FROM PPS             | 4                    |
| I03a                | Subjects being treated with Deferasirox during the 6 months within study participation.   | EXCLUDE FROM PPS             | 4                    |
| I03b                | Subjects being treated with other chelators during the 6 months within study participation.   | EXCLUDE FROM PPS             | 4                    |
| I03c                | Subjects being treated with DFP or DFO or combination (DFP+DFO) at least 6 months continuously.   | EXCLUDE FROM PPS             | 4                    |
| I04                 | Subject is not willing to discontinue current iron chelation therapy at least 5 days prior to the first day and for the duration of the study   | EXCLUDE FROM PPS             | 4                    |
| I05                 | Patients with transfusion-dependent thalassemia (independent of underlying condition) with transfusional iron overload as shown by: a serum ferritin level of <=1000 ng/ml at screening and if available, LIC <= 3 mg Fe/g dw until 6 months prior to screening | INCLUDE IN EVERYTHING        | 0                    |

| Deviation ID | Description of Deviation   | Exclusion in Analyses | Severity code |
|---------------------|---|------------------------------|----------------------|
| I06                 | Patients with non-transfusion-dependent thalassemia with iron overload as shown by: a serum ferritin level of < 800 ng/ml at screening and if available, LIC < 5 mg Fe/g dw until 6 months prior to screening | INCLUDE IN EVERYTHING        | 0                    |
| I07a                | Date informed consent obtained from subject after screening procedures  | INCLUDE IN EVERYTHING        | 0                    |
| I07b                | Date informed consent obtained from parent(s) or legal patient's representative obtained after screening procedures   | INCLUDE IN EVERYTHING        | 0                    |
| M01                 | Use of Prohibited medication as per protocol section 6.3.2.   | EXCLUDE FROM PPS             | 4                    |
| M02                 | Any investigational drug other than the study drug  | EXCLUDE FROM PPS             | 4                    |
| S01                 | Starting dose of deferasirox DT is not compliant with Protocol table 6-2.   | EXCLUDE FROM PPS             | 4                    |
| S02                 | Starting dose of deferasirox FCT is not compliant with Protocol table 7-3.  | EXCLUDE FROM PPS             | 4                    |
| S03                 | Deferasirox DT and/or FCT is not compliant with Protocol table 6-3 based on serum ferritin levels.  | EXCLUDE FROM PPS             | 4                    |
| S04                 | Study dose should be adjusted if there is a change in body weight (increase or decrease) of minimum 10% compare to visit 2 or last dose adjustment due to change in patient's body weight.                    | EXCLUDE FROM PPS             | 4                    |
| S05                 | Patient in period 1 of Core phase received Deferasirox FCT by error (except patients who switched from Deferasirox DT to Deferasirox FCT)   | EXCLUDE FROM FAS             | 1                    |
| S06                 | Patient in period 2 of Core phase or extension phase took Deferasirox DT by error (except patients who switched from Deferasirox FCT to Deferasirox DT).  | EXCLUDE FROM FAS             | 1                    |
| S07a                | Patient re-switched treatment within the same period of the study (that is, patient switched from Deferasirox DT to Deferasirox FCT and the switch back to Deferasirox DT)                                    | EXCLUDE FROM FAS             | 1                    |
| S07b                | Patient re-switched treatment within the same period of the study (that is, patient switched from Deferasirox FCT to Deferasirox DT, and then back to Deferasirox FCT)  | EXCLUDE FROM FAS             | 1                    |

| Deviation ID | Description of Deviation   | Exclusion in Analyses | Severity code |
|--------------|--|-----------------------|---------------|
| S08          | Iron chelation pre-treated patient who is well-managed on treatment with deferoxamine DFO/deferiprone DFP or combination of DFO+DFP did not receive the equivalent deferasirox DT/FCT dose per app. 14.1 | EXCLUDE FROM PPS      | 4             |
| S09          | Dose adjustment (based on Serum ferritin levels and investigator's judgement) in ICT naïve patients done before 4 weeks of study treatment and it was not performed for safety reasons                   | EXCLUDE FROM PPS      | 4             |
| S10          | Dose adjustment (based on Serum ferritin levels and investigator's judgement ) ICT pre-treated patients done before 3 months of study treatment and it was not performed for safety reasons              | EXCLUDE FROM PPS      | 4             |
| S11          | The dose adjustment in deferasirox DT not performed in increments of 5-10 mg/kg/day  | INCLUDE IN EVERYTHING | 0             |
| S12          | The dose adjustment in deferasirox FCT not performed in increments of 3.5-7 mg/kg/day  | INCLUDE IN EVERYTHING | 0             |
| S13          | Deferasirox dose was not temporarily interrupted despite urinary protein/creatinine ratio increases to > 1.0 (mg/mg) in two consecutive second-void urine samples (a minimum of 48h apart)               | INCLUDE IN EVERYTHING | 0             |
| S14          | Deferasirox dose was not temporarily interrupted even though the skin rash persists for > 1 week or becomes more severe  | INCLUDE IN EVERYTHING | 0             |
| S15          | Maximum dose of deferasirox DT is not compliant with Protocol table 6-2.   | EXCLUDE FROM PPS      | 4             |
| S16          | Maximum dose of deferasirox FCT is not compliant with Protocol table 6-2.  | EXCLUDE FROM PPS      | 4             |
| S17          | Dose adjustment of deferasirox DT is not compliant with Protocol table 6-2.  | EXCLUDE FROM PPS      | 4             |
| S18          | Dose adjustment of deferasirox FCT is not compliant with Protocol table 6-2.   | EXCLUDE FROM PPS      | 4             |
| S19          | Patient received incorrect dose due to dispensing error.   | Include in Everything | 0             |
| S20          | Cautious re-initiation of Deferasirox treatment at a lower dose was not done following Study medication interruption due to Increased liver enzyme levels (ALT/AST).                                     | Include in Everything | 0             |

| Deviation ID | Description of Deviation  | Exclusion in Analyses | Severity code |
|--------------|---|-----------------------|---------------|
| S21          | Deferasirox dose reduction by 10 mg/kg/day for the DT formulation and by 7 mg/kg/day for the FCT formulation was not performed following a rise in serum creatinine by 33% above baseline value resulting in a serum creatinine above the ULN on two consecutive visits (a minimum of 7 days apart) | Include in Everything | 0             |
| S22          | Resuming study medication dose is not done according to protocol following treatment interruption for abnormal Serum Creatinine.  | Include in Everything | 0             |

